### **11.4 Cost-Effective Analysis**

A cost-effective model will be constructed to determine if the increased upfront cost of VCE is offset by the decreased cost due to fewer admissions.

## **12 STUDY OVERSIGHT**

A Data Safety Monitoring Board (DSMB) consisting of appropriately qualified independent experts has been appointed by the PI to provide review of data on patient safety and study progress. The membership roster is maintained by Site PI and study coordinator and is available from them as needed. PI will provide reports including adverse events. A summary of DSMB deliberations will be prepared distributed to the subsites to submit to their IRB.

The Data and Safety Monitoring Board provides ongoing evaluation of the study progress including patient accrual and retention, monitoring of adverse events, and the adequacy and efficiency of the analysis plan to discern outcomes that might require study modifications, or result in early cessation of the study due to its benefits or harms. The DSMB does not evaluate the scientific merit or methodology of the study, nor does it directly participate in the execution of a study's protocol, monitor the budget, or approve sub-protocols or other modifications to the study.

The major responsibilities of the Board are:

- To review the data analysis plan and make recommendations for additions or changes to the plan.
- To assess the performance of each participating center and make appropriate recommendations regarding continuation, probationary status, or termination.
- To consider patient accrual, overall study progress (timeline and follow-up participation), adverse effects and patient safety, treatment effectiveness/futility, and proper monitoring and reporting by the study team as these affect the ethical treatment of participants or the ethical conduct of research.
- Report to the PI on any perceived problems with study conduct, enrollment, sample size, and data collection.

### **12.1 Site Visits**

PI and study coordinator will visit all sites a minimum of once annually and each site will engage in monthly calls.

### **12.2 Monthly Reports**

Monthly Recruitment Reports - reports of the number of people screened and enrolled by month. Reports detailing recruitment, baseline patient characteristics, data quality, incidence of missing data and adherence to study protocol.

### **12.3 Annual Reports**

Data and Safety Monitoring Board (DSMB) Reports - The DSMB will prepare a written report which includes patient recruitment, baseline patient characteristics, center performance information with respect to data quality, timeliness of data submission and protocol adherence (in addition to safety and efficacy data). The reports also include adverse events, loss to follow-up and all outcome variables as described previously in this protocol.

### **13 SOURCE DOCUMENTS AND ACCESS TO SOURCE DATA/DOCUMENTS**

Study staff will maintain appropriate medical and research records for this study, in compliance with ICH E6, Section 4.9 and regulatory and institutional requirements for the protection of confidentiality of subjects.

## **14 QUALITY CONTROL AND QUALITY ASSURANCE**

QC procedures will be implemented beginning with the data entry system and data QC checks that will be run on the database will be generated. Any missing data or data anomalies will be communicated to the site(s) for clarification/resolution.

Following written SOPs, the monitors will verify that the clinical trial is conducted, and data are generated, documented (recorded), and reported in compliance with the protocol, GCP, and the applicable regulatory requirements (e.g., Good Laboratory Practices (GLP), Good Manufacturing Practices (GMP)).

The investigational site will provide direct access to all trial related sites, source data/documents, and reports for the purpose of monitoring and auditing by the sponsor, and inspection by local and regulatory authorities.

## **15 ETHICS/PROTECTION OF HUMAN SUBJECTS**

### **15.1 Good Clinical Practices**

The investigator will ensure that this study is conducted in full conformity with the principles set forth in The Belmont Report: Ethical Principles and Guidelines for the Protection of Human Subjects of Research, as drafted by the US National Commission for the Protection of Human Subjects of Biomedical and Behavioral Research (April 18, 1979) and codified in 45 CFR Part 46 and/or the ICH E6.

### **15.2 Institutional Review Board**

The protocol, informed consent form(s), recruitment materials and all participant materials will be submitted to the IRB for review and approval. Approval of both the protocol and the consent form must be obtained before any participant is enrolled. Any amendment to the protocol will require review and approval by the IRB before the changes are implemented in the study.

### **15.3 Informed Consent Process**

Informed consent is a process that is initiated prior to the individual agreeing to participate in the study and continues throughout study participation. Extensive discussion of risks and possible benefits of study participation will be provided to participants and their families, if applicable. A consent form describing in detail the study procedures and risks will be given to the participant. Consent forms will be IRB-approved, and the participant is required to read and review the document or have the document read to him or her. The investigator or designee will explain the research study to the participant and answer any questions that may arise. The participant will sign the informed consent document prior to any study-related assessments or procedures. Participants will be given the opportunity to discuss the study with their surrogates or think about it prior to agreeing to participate. They may withdraw consent at any time throughout the course of the study. A copy of the signed informed consent document will be given to participants for their records. The rights and welfare of the participants will be protected by emphasizing to them that the quality of their clinical care will not be adversely affected if they decline to participate in this study. The consent process will be documented in the clinical or research record.

### **15.4 Exclusion of Women, Minorities, and Children (Special Populations)**

All adults will be included. Children will be excluded because upper GI bleed is typically a disease of adults.

### **15.5 Participant Confidentiality**

All records will be confidential. Subjects will not be identified in any reports or publications of this study. It is possible that representatives of regulatory agencies and from the study's sponsor may come to (the university/hospital) to review study information. In that situation, copies of the relevant parts of the study records will be released with all identifying information removed. Access to study records will be limited to those who need the information for purposes of this study, as well as your health care providers should they need access to the information. All records are kept in a secure location and access is limited to research study personnel.

## **16 DATA HANDLING AND RECORD KEEPING**

### **16.1 Data Management Responsibilities**

Each participating site will maintain appropriate medical and research records for this trial, in compliance with ICH E6 and regulatory and institutional requirements for the protection of confidentiality of participants. As part of participating in this study, each site will permit authorized representatives of the PI to examine (and when permitted by applicable law, to copy) clinical records for the purposes of quality assurance reviews, audits, and evaluation of the study safety, progress, and data validity.

Source data are all information, original records of clinical findings, observations, or other activities in a clinical trial necessary for the reconstruction and evaluation of the trial. Examples include, but are not limited to, hospital records, clinical and office charts, laboratory notes, memoranda, recorded videos of upper Gi tract, recorded data from automated instruments, copies or transcriptions certified after verification as being accurate and complete, microfiches, photographic negatives, microfilm or magnetic media, x-rays, and participant files and records kept at the pharmacy, at the laboratories, and medico-technical departments involved in the clinical trial. It is acceptable to use CRFs as source documents. Except for videos, all data will be collected on CRFs.

Study participation will also be recorded in the medical record to ensure that anyone who would access the patient medical record has adequate knowledge that the patient is participating in a clinical trial.

### **16.2 Data Capture Methods**

Data will be captured both via hand written source documents and a centralized web-based data entry system. The centralized web system will be Redcap and will be administered by GWUH.

### **16.3 Schedule and Content of Reports**

The recruitment and follow-up periods begin in April 2017 and continue through April 2018. Data queries are generated and resolved during this time period through June 2018. Data close-out will be performed immediately following end of recruitment period.

### **16.4 Study Records Retention**

Study records will be maintained for at 3 years post study closure and per IRB specifications.

### **16.5 Protocol Deviations**

Protocol deviations will be maintained through protocol deviations source documentation that is entered into the centralized databased. Protocol deviations will also be reported directly to study PI within 24 hours.

## **17 PUBLICATION/DATA SHARING POLICY**

This study will comply with the [NIH Public Access Policy](#), which ensures that the public has access to the published results of NIH funded research. It requires scientists to submit final peer-reviewed journal manuscripts that arise from NIH funds to the digital archive [PubMed Central](#) upon acceptance for publication.

## APPENDICES

### 18.1 APPENDIX A: Schedule of Events

2017

December - February Consensus building. Protocol Development

2017

January-December IRB submission at all sites

January-December Contract between primary site GW and all enrolling sites

January- December DSMB formation, steering committee convene, central CE reading team call schedule established for March 2017 to March 2018

2018

March CE training and Site Visit by PI and team

April Enrollment kick off

April-April Monthly Calls for entire team. Status reports.

2019

April Target Enrollment Reached, End recruitment

April DSMB report prepared

June Data Cleaning

August First manuscript Draft Prepared

September Manuscript Submitted (To be discussed: Dissemination plan.)

## **18.2 APPENDIX B – Document List**

Cheer 1: Screening Log

Cheer 2: Eligibility

Cheer 3: Patient Data Collection Form

Cheer 4: Patient Screening; GBS Score

Cheer 5: Patient Lab Values Pre- PillCam

Cheer 6: Patient Lab Values Post-PillCam

Cheer 7: Video Capsule Endoscopy Data Collection sheet

Cheer 8: EGD Data Collection Sheet

Cheer 9: Patient Satisfaction Day 7 and Day 30

Cheer 10: Patient Follow up Day 7 and Day 30

Cheer 11: Patient Chart Review

Cheer 12: Adverse Event Form/ Serious Event Form

Cheer 13: Protocol Deviation

### 18.3 Screening Log

#### CHEER 1 SCREENING LOG

Screen #	Project Name: CHEER				Site# + PI Name		GW + [name]
	Screening Type	Patient Initials	Pre-Screen Date	Pass/Fail	Screen Failure Reason	Notes	
1	Pre-Screen	AB	4/1/2017	Fail	Exclusion #1- Hemodynamic Instability		
2							
3							
4							
5							
6							
7							
8							
9							
10							
11							
12							
13							
14							
15							
16							
17							
18							
19							
20							
21							
22							
23							
24							
25							
26							
27							
28							
29							
30							
31							
32							
33							
34							
35							
36							
37							
38							
39							
40							
41							
42							

#### 18.4 Patient Screening

## Patient Screening

Record ID \_\_\_\_\_ Date of Screening \_\_\_\_\_ Initials of Person Completing Form \_\_\_\_\_

**1. Age of 18 or older**

Yes No (Must be YES to be eligible for study)

**2. Evidence of likely acute upper GI bleed (melena, hematemesis (bright red or coffee-ground) in the last 48 hours?**

Yes No (Must be YES to be eligible for study)

**3. Treating ED Physician is amenable to admission or discharge based on randomization and/or results of video capsule endoscopy.**

Yes No (Must be YES to be eligible)

**4. Upper GI Bleed with hemodynamic instability (BP<90 mmHg, pulse>120 beats per minute, and Hgb<9 g/dL)**

Yes No (Must be NO to be eligible for study) 5. High Risk Upper GI Bleed (Glasgow Blatchford Score  $\geq$  6)

Yes No (Must be NO to be eligible for study) **5. Presumed pregnant, trying to conceive or breastfeeding**

Yes No (Must be NO to be eligible for study)

**6. Signs, symptoms, or history of liver cirrhosis or liver failure**

Yes No (Must be NO to be eligible for study)

**7. Signs, symptoms, or history of decompensated heart failure or congestive heart failure**

Yes No (Must be NO to be eligible for study)

**8. Known history of gastric cancer**

Yes No (Must be NO to be eligible)

**9 Known history of gastric or esophageal varices**

Yes No (Must be NO to be eligible for study)

**10. GI surgery within the last 6 months**

Yes No (Must be NO to be eligible for study)

**11. Prior enrollment in the CHEER Study**

Yes No (Must be NO to be eligible for study)

**12. Prisoner or Ward of State**

Yes No (Must be NO to be eligible for study)

**13. Trouble swallowing, suspected bowel obstruction or perforation, per treating clinician**

Yes No (Must be NO to be eligible for study)

**14. Past UGI tract surgery (e.g., Billroth I or II, esophagectomy, gastrectomy, bariatric procedure) that changes Gastrointestinal anatomy**

Yes No (Must be NO to be eligible for study)

**15. Known history of gastroparesis, esophageal stricture or Crohn's disease**

Yes No (Must be NO to be eligible for study)

**16. Altered mental status that limits the ability to swallow a capsule**

Yes No (Must be NO to be eligible for study)

**17. Expected to have Magnetic Resonance Imaging (MRI) examination within 7 days**

Yes No (Must be NO to be eligible for study)

**18. Consumed medications within the past 12 hours that may coat the upper GI tract such as antacids or sucralfate or Maalox and potentially limits capsule visualization**

Yes No (Must be NO to be eligible for study)

**19. Patient either refuses or is unable to get traditional EGD**

Yes No (Must be NO to be eligible for study)

**20. Patient does not have reliable contact information – no phone, no permanent address**

Yes No (Must be NO to be eligible for study)

**21. Patient refuses**

Yes No (Must be NO to be eligible for study)

**22. Unable to provide written consent**

Yes No (Must be NO to be eligible for study)

[figure not shown]
**23. Non-English speaker**

Yes No (Must be NO to be eligible for study)

**24. Suspected middle or lower GI bleeding**

Yes No (Must be NO to be eligible for study)

If eligible and consented, affix VCE label here.

### 18.5 Patient Data Collection

## Patient Data Collection

Initials of Person Completing Form \_\_\_\_\_ Time \_\_\_\_\_

**Gender** Male Female

**Race** White Black Asian Native American Other If other, please indicate

**Ethnicity (self-report)** Hispanic Not Hispanic

**Date and time patient last ate** \_\_\_\_\_

**Have you had any bloody or black "tar" stools in the past 24 hours?** Yes No

**Have you had bloody or coffee ground vomit in past 24 hours?** Yes No

**Have you felt weak or light headed in past 24 hours?** Yes No

**Have you passed out or lost consciousness in the past 24 hours?** Yes No

#### **How long ago did this episode of bleeding first start?**

Less than 4 hours

Between 4 and 12 hours

Between 12 and 24 hours

Between 1-2 Days

More than 2 Days

Unsure

**Any allergies?** Yes No

Please list allergies \_\_\_\_\_

**Is patient on any current medications?** Yes No

Please list medications \_\_\_\_\_

**Currently taking Proton pump inhibitor (PPI) Antacids?**

Examples include Prilosec (omeprazole), protonix (pantoprazole), prevacid (lansoprazole), aciphex (raeprazole), nexium (esomeprazole)? Yes No

**Do you take any NSAIDS? Examples include aspirin, ibuprofen, Aleve, Advil, Motrin?** Yes No

#### **Do you have any of the following medical problems?**

Heart attack OR Heart disease	Ulcer or Gastritis or Acid Reflux
Diabetes Mellitus	Hemorrhoids
Cancer that spread	Prior abdominal surgery OR pelvic surgery
Kidney Failure OR on dialysis	inflammatory bowel disease (Crohn's OR Ulcerative Colitis)
Previous Smoker OR Active Smoker	Bowel Obstruction
Liver Disease OR Liver Cirrhosis	Other: _____

## 18.6 Patient Screening: GBS Score

**Gender** Male Female

**Blood Urea (mg/dL)**

<18.2 (0 points)

18.2-22.3 (2 points)

22.4-28 (3 points)

28-70 (4 points)

>70 (6 points)

**Hemoglobin (g/dl)**

>13.0 (0 points for either gender)

12.0-13.0 (1 point male 0 point female)

9.0-12.0 (3 points male 1 point female)

< 9.0(6 points for either gender)

**Systolic blood pressure (mmHg)**

>110 (0 points)

100-109 (1 point)

90-99 (2 points)

< 90 (3 points)

**Heart rate higher than 100 bpm** Yes (1 point) No (0 points)

**Presentation with syncope** Yes (2 points) No (0 points)

**Cardiac Disease (echocardiography evidence)** Yes (2 points) No (0 points)

**Hepatic disease (chronic, acute liver disease)** Yes (2 points) No (0 points)

**Presentation with melena** Yes (1 point) No (0 points)

GBS Score \_\_\_\_\_

(NOTE: GBS <6 to be eligible for the study)

### **18.7 Patient Lab Values Pre PillCam**

Record ID \_\_\_\_\_

Date/Time Collected \_\_\_\_\_

Hemoglobin \_\_\_\_\_ g/dL

### **18.8 Patient Lab Values Post PillCam**

Record ID \_\_\_\_\_

Date/Time Collected \_\_\_\_\_

Hemoglobin \_\_\_\_\_ g/dL

### 18.9 PillCam Data Collection

## Video capsule endoscopy (PillCam) data collection

Date/Time PillCam given \_\_\_\_\_ Initials person filling out form \_\_\_\_\_

Provider reading PillCam \_\_\_\_\_

Real Time or Retrospective Read \_\_\_\_\_

### ON THE ACCOMPANYING VIDEO CAPSULE ENDOSCOPY IS THERE EVIDENCE OF THE FOLLOWING? (Circle all that apply)

- a. Clean stomach and duodenum, i.e., no fresh blood or coffee ground
- b. Upper GI pathology non-causative/ incidental.
- c. A LOW grade non-Variceal lesion (Forrest IIc, III)
- d. A HIGH Grade Non-Variceal Lesion (Forrest Ia, Ib, IIa or IIb)
- e. Coffee ground blood
- f. Fresh blood or evidence of active bleeding
- g. Varices (either gastric or esophageal) or Variceal Hemorrhage
- h. Other sources of bleeding

-Mallory-Weiss

-Angiodysplasia

-Gastritis

-Esophagitis

-Tumor

#### i. If there is a bleeding source, where is it?

-Esophagus

-Stomach

-Duodenum

-None detected

#### j. Did the capsule pass the pylorus before battery life expired (and does not detect lesion in stomach or esophagus.) Yes No

#### k. Based on your findings, would you recommend endoscopic hemostasis?

Yes

No

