In a study of 25 subjects, VCE interpretation by emergency physicians demonstrated excellent agreement with gastroenterologists for the presence of fresh or coffee-ground blood (0.96 overall agreement;  $\kappa \geq 0.90$ ) [7]. In another study, 126 emergency physicians were asked to look at standardized videos from ED patients who presented with acute UGIB. Compared with expert gastroenterology-adjudicated interpretation, the sensitivity of ED physicians to detect blood was 0.94% (95% CI: 91%-96%) and specificity was 87% (95% CI: 80%-92%) [10].

Gastrointestinal hemorrhage is a common emergency condition, and the severity ranges from benign to life threatening. Risk stratification of acute UGIB is challenging in the ED because traditional diagnostic approach using the physical exam, lab testing and radiographic studies is too nonspecific to be used without adjunctive endoscopy. As a result, many patients with an ultimately benign clinical course are admitted to the hospital and incur considerable costs. Without an ED-based endoscopy, alternative means to risk stratify patients with signs of UGIB include performing nasogastric aspiration, which is uncomfortable for patients [11], using clinical decision rules, such as the Rockall Risk Score and Glasgow-Blatchford Score, or admitting all patients with suspected upper gastrointestinal bleed for endoscopy [12].

Most endoscopy capsules are manufactured for use in the small bowel, but the esophageal capsule endoscope (PillCam UGI, Medtronic) is designed to visualize the upper gastrointestinal tract. The esophageal VCE is equipped with 2 cameras at either end that take 35 pictures per second for 30 minutes. Initial studies with early-generation esophageal VCE demonstrated a sensitivity of 92% and specificity of 95% to diagnose chronic reflux esophagitis [13]. In addition, the sensitivity and the specificity were found to be 97% and 99%, respectively, for the diagnosis of Barrett esophagus and 89% and 99%, respectively, for diagnosis of esophagitis [13].

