In all ED studies that have been conducted for acute upper gastrointestinal hemorrhage, VCE has performed well when it travels through the pylorus. However, several high-risk lesions were missed if the VCE did not travel through the pylorus before the battery expired. The time to pass the pylorus is variable. At 60 minutes, 98% of capsules visualize the duodenum [6]; when the battery life is only approximately 20-30 minutes, approximately 50% visualize the duodenum (12/25 [7], 44/83 [8], and 7/12 [14]). In one study, the single missed active bleeding occurred in a patient who was bleeding in the post-pyloric duodenum and in whom the VCE battery expired before reaching the post-pyloric region [7]. For standard EGD, the use of pro-kinetic agents such as erythromycin or metoclopramide has improved mucosal visualization and has been increasingly used before the procedure. This strategy, combined with 60 minutes of visualization, will likely increase the accuracy of VCE as well.

The cost of the VCE is an important factor that affects future use in the ED. The physician Medicare national average fee is \$705 for the PillCam UGI and \$50 for the professional fee. Although expensive, VCE may be cost-effective if it safely reduces hospital admissions or emergency EGD. For comparison, in 2011, 236,000 patients received an EGD (International Classification of Diseases, Ninth Revision code 45.13) in the hospital for an upper UGIB, the median length of stay was 4.0 days, and the median charges were \$23,549.17 [12].

A decision-analytic model showed that VCE is cost effective for low- to moderate-risk patients despite increased upfront costs compared with clinical decision rules or nasogastric tubes. The use of VCE in the ED can potentially lead to more patients being safely discharged from the ED. The hospital admission is the single most expensive decision made by an emergency physician. Chandran et al [8] showed that the higher sensitivity of VCE compared with the Glasgow-Blatchford Score would have saved \$1691 per VCE by increasing the number of patients who could receive an outpatient EGD.

Currently, the VCE does not replace the need for traditional EGD when hemostasis or biopsy is needed. Technological advancements may allow a VCE operator to control movement of the capsule, collect biopsy samples, and perform therapeutic functions.

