#### 3.2 Study Outcome Measures

3.2.1 Primary Outcome: (1) Percent Discharged Home. Assumption is that 100% of Active Control (AC) group will be admitted.

3.2.2 Secondary Outcome: Sensitivity and specificity of VCE compared to EGD. *Endpoints will be defined in the following way:*

Positive Video Capsule Endoscopy will be defined as:

1. Fresh blood or evidence of active bleeding visualized in upper GI tract.
2. Coffee ground blood visualized in upper GI tract, but no active bleeding seen.
3. A High Grade Non-Variceal Lesion (Forrest Ia, Ib, IIa or IIb).
4. Signs of Variceal Hemorrhage.
5. Signs of malignancy visualized in upper GI tract.

Negative VCE:

5. Clean stomach and duodenum, no fresh blood or coffee ground.
6. Upper GI pathology non-causative/ incidental.
7. A low grade non-Variceal lesion (Forrest IIc, III).

An Inconclusive VCE:

8. Any capsule that does not pass the pylorus before battery life is expired (and does not detect lesion in stomach or esophagus).

Positive EGD

1. Fresh blood or evidence of active bleeding.
2. Coffee ground but no active bleeding seen.
3. A High Grade Non-Variceal Lesion (Forrest Ia, Ib, IIa or IIb).
4. Signs of Variceal Hemorrhage.

Negative EGD

5. Clean stomach and duodenum, no fresh blood or coffee ground.
6. Upper GI pathology non-causative/ incidental.
7. A low grade non-variceal lesion (Forrest IIc, III).

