### **11.3 Final Analysis Plan**

The analysis will be conducted in several stages. First, we will compare the baseline characteristics of the two study groups to determine if randomization was successful. We will also compare the baseline characteristics of the study samples by enrollment site. Second, we will compare the VCE and EGD results and classify all study subjects according to whether there is a high versus low risk lesion present. The VCE and EGD results may differ because they are not being performed at the same time and GI bleeds can resolve or change so it is unlikely that there will be perfect agreement between the two modalities. In cases where one modality identifies a low risk lesion and the other one a high-risk lesion, we will classify the lesion as high risk. If the VCE could not adequately visualize the tract, we will classify the results according to the EGD. We will compare the sensitivity and specificity of VCE and EGD for identifying high risk lesions. Finally, we will separately compare the admission rates of high-risk lesions and low risk lesions between the two study groups. We will compare admission rates aggregated across the four study centers as well as within each study center.

For tertiary outcomes, we will compare the outcomes by study group using a chi-square test statistic if the outcome is categorical such as the presence of an adverse event and a t test (normally distributed) or median test (non-normally distributed) if the outcome is continuous such as hospital or ED length of stay.

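### Capsule form item j merges pyloric passage with absence of a lesion, and the inconclusive definition lets some capsules that never saw the duodenum count as negative

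*Combined protocol and SAP*

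**What the plan says.** Four places in the combined protocol and SAP bear on this.

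- **Section 18.9, item j** (VCE data form) asks, with a single answer: "Did the capsule pass the pylorus before battery life expired (and does not detect lesion in stomach or esophagus.) Yes No".
- **Section 3.2** defines an inconclusive VCE as "Any capsule that does not pass the pylorus before battery life is expired (and does not detect lesion in stomach or esophagus". Its negative list includes "Upper GI pathology non-causative/ incidental" and "A low grade non-Variceal lesion (Forrest IIc, III". Neither entry requires that the duodenum was seen.
- **Section 11.3** has a rule for poor views: "If the VCE could not adequately visualize the tract, we will classify the results according to the EGD". It also classes a subject as high risk if either modality shows a high-risk lesion. It then compares VCE and EGD on sensitivity and specificity, without saying where an inconclusive VCE goes.
- **Section 2.1** describes an esophageal capsule whose cameras "take 35 pictures per second for 30 minutes" and reports that "when the battery life is only approximately 20-30 minutes, approximately 50% visualize the duodenum (12/25 [7], 44/83 [8], and 7/12 [14". The same section gives 98% duodenal visualization at 60 minutes and looks ahead to 60 minutes of viewing.

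**The concern.** Section 2.1 says that VCE performed well in the emergency department studies when the capsule passed the pylorus, and that several high-risk lesions were missed when it did not. Whether a capsule got through is therefore the first thing one needs to know about a negative result. Item j does not record it cleanly, and the Section 3.2 wording lets some incomplete examinations into the negative group. At stake is the named secondary outcome: sensitivity and specificity could mix complete and incomplete negatives. The accuracy figures that Section 2.1 quotes for capsules that reached the duodenum would then have no clean counterpart in this trial.

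**Working it through.** **1. What each answer to item j means.** Item j can be read in three ways: (A) literally, as passage and no lesion; (B) as passage alone, ignoring the bracket; (C) as the Section 3.2 inconclusive definition from which the bracket is borrowed. The last column applies the Section 3.2 lists.

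| Passed pylorus | Finding in stomach or esophagus | A | B | C | Section 3.2 label |
|---|---|---|---|---|---|
| Yes | None | Yes | Yes | No | Negative, or Positive if the duodenum shows a positive finding |
| Yes | Low-grade or incidental lesion | No | Yes | No | Negative |
| Yes | High-grade lesion | No | Yes | No | Positive |
| No | None | No | No | Yes | Inconclusive |
| No | Low-grade or incidental lesion | No | No | No | **Negative** |
| No | High-grade lesion | No | No | No | Positive |

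Under reading A, a No with no lesion circled does isolate the inconclusive group. A No with a gastric or esophageal lesion circled does not separate passed from not passed. If some readers use C, the inconclusive group is ticked Yes instead, so even that group is unreliable across readers. The row in bold is negative under all three readings.

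**2. Other items on the form.** Item a (clean stomach and duodenum) implies passage, but only for a clean examination. Item i asks for a location only if there is a bleeding source. Neither replaces a passage field.

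**3. The protocol's passage figures.** 12/25 = 48.0%, 44/83 = 53.0% and 7/12 = 58.3%. Pooled: (12 + 44 + 7)/(25 + 83 + 12) = 63/120 = 52.5%, which agrees with the stated figure of about 50%. Non-passage is then 57/120 = 47.5% at 20–30 minutes, and 100% − 98% = 2% at 60 minutes.

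**4. Number of capsules.** Assume 50 capsule patients (100 subjects at 1:1; the ratio is not stated).

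- At 2% non-passage: 50 × 0.02 = 1 capsule.
- At 47.5%: 50 × 0.475 = 23.75, about 24 capsules.

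The documents do not give the share of these with only a low-grade or incidental upstream lesion. Over an assumed 10% to 50%, the number labelled negative without a view of the duodenum is 0.1 to 0.5 at 2% non-passage, and 2.4 to 11.9 at 47.5%.

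**5. What one such capsule does to sensitivity.** Assume 10 EGD-positive patients in the capsule arm (20% of 50, the upper end of the high-risk share in Section 11.2) and all others detected. One mislabelled capsule with a positive EGD gives 9/10 = 90% if counted negative and 9/9 = 100% if set aside as inconclusive, a difference of 10 points. One with a negative EGD enters specificity as a true negative although the examination was incomplete.

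**6. Effect on the risk classification in Section 11.3.** If the VCE is labelled negative, the either-modality rule makes the subject high risk exactly when the EGD is high risk. If it is inconclusive and handled by the fallback, the EGD decides. When an EGD exists, the two routes give the same class.

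**The case against.** Much can be said for the plan. The coordinator watches for pyloric passage on the real-time viewer (Section 4.4), videos are source data (Section 16.1), and offsite gastroenterologists re-read every VCE (Section 4.4). A literal reading of item j still identifies non-passing capsules with no lesion. Accuracy is not the primary objective, as Section 4.4 says outright. The pro-motility agent given before ingestion, with longer recording, may make non-passage rare.

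Most of this stands, and it rules out three stronger readings that a reader might infer.

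- *That incomplete capsules cannot be identified at all.* They can be, from the videos, and in part from the form.
- *That Section 11.3 puts the EGD result in place of the VCE result in the accuracy table, so that incomplete capsules agree with EGD by construction.* The fallback sentence belongs to the step that classifies subjects by lesion risk, and accuracy comes in a later sentence. The text leaves the matter open and does not say that the substitution is made.
- *That every incomplete capsule is a missed lesion.* A non-passing capsule that shows a high-grade gastric lesion is positive under Section 3.2, so an all-capsule sensitivity computed by counting all incomplete capsules as failures has no support.

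The objection does not remove the defect. Section 16.1 puts all data except videos on case report forms, and none of those shown has a clean passage field. The VCE form also has a field for real-time or retrospective reading, so a re-read entered on it would inherit the same ambiguity. Recovery from video works only once the fields are separated. The negative label in the bold row comes from the definition, so a better form alone would not change it.

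**Conclusion.** The concern holds in limited form. Item j does not reliably give pyloric passage when a gastric or esophageal lesion is recorded or when readers interpret it differently; the stored videos can supply it. Separately, the Section 3.2 exemption covers a lesion of any grade, so a non-passing capsule with only incidental or Forrest IIc/III findings is negative without a view of the duodenum. This affects VCE sensitivity and specificity. It does not change the high/low-risk classification when an EGD exists, and it changes no sample size or power.

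The size is uncertain. Non-passage of 2% to 47.5% means about 1 to 24 of an assumed 50 capsules, and only an undocumented share of those is mislabelled. The range is wide because Section 2.1 gives both 30 and 60 minutes without saying which recording time applies to this trial.

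**What to change.** 1. **Form (Section 18.9).** Replace item j with two fields: *Capsule passed pylorus before recording ended: Yes/No* and *Positive finding in esophagus or stomach: Yes/No*. For capsules already read, complete both from the stored videos.
2. **Definition (Section 3.2), for the accuracy analysis.** Change the exemption so that a non-passing capsule is inconclusive when it *shows none of the findings listed under Positive VCE*. Refer to the list by name, because Section 3.2 uses the number 5 for both a positive and a negative finding.
3. **Analysis (Section 11.3).** State that the EGD fallback applies only to the high/low-risk classification of subjects and is never used as the VCE result. Keep inconclusive as its own VCE row against EGD. Report sensitivity and specificity among complete capsules and among all capsules ingested.
4. **To be reconciled by the study team.** How an inconclusive VCE relates to disposition (Sections 3.2 and 4.4), and the 30- and 60-minute recording times in Section 2.1.

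The cost is one form edit, one definition edit, a review of stored videos for capsules already read, and one extra table. The all-capsule sensitivity may look less favorable.
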